### 9.2.2 Pre-dose (relative time: Day 1)

Participants will arrive at the study site for their scheduled study visit at the designated time preceding study drug administration. The following measures / actions will be carried out:

- Informed consent
- Review of inclusion- / exclusion criteria
- Allergy Profile Questionnaire

### **9.2.3 Randomization**

No randomization schedule will be used.

### **9.2.4 Treatment**

#### **Treatment / Assessment Phase**

Prior to each assessment, adequate and appropriate training will be conducted to ensure participants understand the task and how to use the study scales. An appropriate nurse practitioner will be on site during the entire dosing period.

#### **Visit 1 (Day 1)**

- One test product will be provided in a dosing cup to each participant who will then be asked to completely chew completely before swallowing. Participants cannot drink water until end of visit.
- Study staff initiates timer as soon as the study medication is administered
- Participant will be asked to indicate on the case report form (CRF) if he/she perceives a cooling sensation in the mouth, nose and throat at 10 seconds, 30 seconds and 1 minutes post ingestion of test product
- After the 1-minute time point, participants will be asked to complete a brief questionnaire on the sensory attributes of the test product. Participants will be allowed four (4) minutes to complete the questionnaire.
- Following the completion of the questionnaire, participants will continue to evaluate perception of cooling sensation in the mouth, nose and throat at 5 minute intervals, starting at the 5 minute time point for 60 minutes
- Following completion of all study assessments, participants will be asked open ended questions which will be used for learning purposes
- Adverse events, if applicable, will be recorded
- Participants will be reminded to report any unusual or unexpected medical changes within the 24 hour period following administration of the study medication to site personnel

#### **Follow- Up**

At the End of Visit 1, if a participant has an ongoing adverse event, he/she will be contacted during the following week after discharge from the study site.

## **9.3 Population Characteristics**

### **9.3.1 Demographics**

The following information will be collected for the Demographics

- Year of birth
- Sex

- Race/ethnicity

### **9.3.2 Medical History**

Medical history findings (i.e. previous diagnoses, diseases or surgeries) meeting all criteria listed below will be collected as available to the investigator:

- Start before signing of the informed consent
- Considered relevant for the participant's study eligibility.

Detailed instructions on the differentiation between (i) medical history and (ii) adverse events can be found in Section 9.5.1.

### 9.3.3 Allergy Profile Questionnaire

The following questionnaire will be completed by subjects prior to dosing.

#### Allergy Profile Questionnaire

1. What type of allergies have you experienced in the last 12 months? (Select all that apply)

- a. Seasonal allergies
- b. Dust or dust mite allergies
- c. Pet/ animal allergies
- d. Mold
- e. Other \_\_\_\_\_

2. CCI [Redacted]  
[Redacted]  
[Redacted]  
[Redacted]  
[Redacted]  
[Redacted]  
[Redacted]

3. CCI [Redacted]  
[Redacted]

### 9.4 Study Assessment

The following study specific assessments will be performed by the participants during this study.

#### 9.4.1 Cooling Time Point Assessment

Participants will be instructed to complete as follows:

“Please indicate at each time point whether you perceive a cooling sensation in the mouth (1), nose (2), throat (3) or (4) No Sensation Felt.

Time	Cooling in the mouth (1)	Cooling in the nose (2)	Cooling in the throat (3)	No Sensation Felt (4)
Immediate (10 seconds)				
30 seconds				
1 minute				
Complete the sensory attributes questionnaire (see questionnaire below)				
5 minutes				
10 minutes				
15 minutes				
20 minutes				
25 minutes				
30 minutes				
35 minutes				
40 minutes				
45 minutes				
50 minutes				
55 minutes				
60 minutes				

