## 6. STUDY POPULATION

### 6.1 Inclusion Criteria

Only participants who meet all of the following eligibility criteria will be eligible for the study:

1. Capable of understanding and providing written informed consent and confidentiality including signatures.
2. Female or male adults aged 18 to 65 years of age inclusive (recruitment to ensure that no less than approximately 40% of each gender is represented in the study population)

3. Be in good general health
4. Previous sufferers of self-reported upper respiratory allergies who at the time of the study are either asymptomatic, symptomatic but not treating and agree to use study medication or symptomatic and treating with an allergy medicine that is not an antihistamine
5. Agree to not use antihistamine products 24 hours before and after the treatment (see medication exclusion list, [Appendix 1](#))
6. Willing to comply with appropriate instructions provided to complete the study
7. Willing to avoid eating food or candy (other than crackers consumed during testing), drinking any liquid other than water, gum chewing and teeth brushing one hour prior to testing
8. Willing to follow and to adhere to the testing instructions as set forth in this protocol.

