## **6.3 Lifestyle/Dietary Restrictions**

Participants will be restricted from eating food or candy (other than crackers consumed during testing), drinking any liquid other than water, gum chewing and teeth brushing one hour prior to testing. During testing, participants cannot drink any liquid including water, chew gum or brush their teeth until the end of the visit; otherwise, there are no lifestyle restrictions.

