## 9. PROCEDURES AND VARIABLES

### 9.1 Tabular Schedule of Evaluations

	Pre- Study (-30 Day to -1 Day)	Visit 1 (Day 1)										
		Baseline	10 s.	30 s.	1 min.	(4 min interval)	5 min.	10 min.	15 min.	... *	60 min.	End of Study and Follow- up
Pre-Screening	X											
Informed Consent		X										
Medical/Medicat ion History		X										
Demographics		X										
Verification of Inclusion & Exclusion Criteria		X										
Allergy Profile Questionnaire		X										
Test Product Administration		X										
Cooling Time Point Assessment			X	X	X		X	X	X	X	X	
Sensory Attributes Questionnaire						X						
Open Ended Questions												X
Adverse Event Monitoring		X	X	X	X	X	X	X	X	X	X	X †

(...)\* Time points are at 5-minute intervals up to the last time point.

†At the End of Study, if a participant has an ongoing adverse event, the adverse event will be monitored and recorded and the participant will be contacted during the following week after discharge from the study site.

s= seconds, min= minutes

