#### Screening Phase

**Note: No screening procedures may be performed unless written informed consent has been obtained.** During the screening period, the study staff will screen potential participants to verify they meet the study's eligibility criteria. Not all participants may fulfill the inclusion / exclusion criteria, so a higher number of participants than needed will be asked to participate in the screening examinations. If the (first) screening procedures start on the same day the participant signs the informed consent form/assent (ICF), the time of the participant's signature must be recorded in the participant's file.

After obtaining the participant's signature on the consent form, the below listed screening procedures will be performed and the respective results will be assessed on the day of the first study drug administration:

- allocation of participant identification ([see Section 6.6](#))
- demographic data
- review eligibility
- questioning for special behavior (e.g., eating food or candy, chewing gum, or brushing teeth within one (1) hour prior to enrollment on testing day and not willing to abstain from this at least 1 hour prior to testing)
- participation in previous research studies

No participant will be assigned a participant number unless adherence to all selection criteria as given in Section 6.1 and Section 6.2 is established.

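### With no pre-dose cooling reading and no comparator, cooling already felt before the tablet is scored as a 10-second onset; the effect falls mainly on the secondary onset claim

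*Combined protocol and SAP*

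**What the plan says.** - **The reading.** The instruction in 9.4.1 is "Please indicate at each time point whether you perceive a cooling sensation in the mouth (1), nose (2), throat (3", with a fourth column for no sensation. It asks about perceived cooling, not about change or about the tablet as the source. The first row is "Immediate (10 seconds"); there are 15 rows, ending at 60 minutes.
- **The schedule.** In 9.1 the row "Cooling Time Point Assessment" is empty under Baseline and has its first mark at 10 seconds. The pre-dose list in 9.2.2 has consent, "Review of inclusion- / exclusion criteria" and the allergy questionnaire.
- **Time zero.** From the Visit 1 description in 9.2.4: "Study staff initiates timer as soon as the study medication is administered".
- **Design.** One product, not randomized, no comparator (Synopsis, 7.2).
- **Restrictions.** Section 6.3 bars food and candy, and also "drinking any liquid other than water, gum chewing and teeth brushing one hour prior to testing". Water is allowed until testing with no limit on temperature. Mouthwash, breath sprays and breath strips are not named, and 6.3 states that no other lifestyle restrictions apply.
- **Analysis.** Under 10.3 the mean time of first perceived cooling becomes the onset claim, and the mean time to which cooling lasts becomes the duration claim. Participants who never report cooling are set to 60 minutes, and are also analysed as censored by Kaplan-Meier. Both variables are secondary. No correction for the pre-dose state is described.

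**The concern.** In a single-arm study the only available reference for a sensation is the participant's own state before dosing, and the plan does not record it. Someone whose mouth, nose or throat already feels cool will truthfully tick cooling at 10 seconds. The data cannot separate that tick from one caused by the tablet. Because 10 seconds is the earliest time the form can record, such a participant can only pull the onset figure earlier.

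A pre-dose row would also show how often participants tick cooling when nothing has been given, which no other part of the design measures. Once the tablet has been chewed, the missing reading cannot be recovered.

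**Working it through.** **Is there a figure to reproduce?** No. Section 10.4 gives 400 participants with no rate, effect or power, and this point does not depend on the sample size. The documents give no background rate, so b is an assumption, shown from 1% to 20%. With 400 participants, each 1% is 4 people and 5% is 20.

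**Onset.** A participant with background cooling is recorded at 10 s = 10/60 min instead of the true onset T. So:

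fall in mean onset = b × (T − 10/60)

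| b | T = 1 min | T = 5 min | otherwise never, set to 60 min |
|---|---|---|---|
| 1% | 0.01 | 0.05 | 0.60 |
| 5% | 0.04 | 0.24 | 2.99 |
| 10% | 0.08 | 0.48 | 5.98 |
| 20% | 0.17 | 0.97 | 11.97 |

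For example, 0.05 × (5 − 0.167) = 0.24 min and 0.05 × (60 − 0.167) = 2.99 min. The last column is an upper limit: it assumes that everyone affected would otherwise have been imputed at 60 minutes.

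**Two assumed profiles** (illustrations only), with background cooling spread evenly over participants:

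- *Mouth:* 60% at 10 s, 25% at 30 s, 10% at 1 min, 5% never. Mean = 0.10 + 0.125 + 0.10 + 3.00 = 3.33 min. At b = 10%: 0.9 × 3.325 + 0.1 × 0.167 = 3.01 min.
- *Nose:* 10% at 10 s, 15% at 30 s, 15% at 1 min, 20% at 5 min, 40% never. Mean = 0.017 + 0.075 + 0.15 + 1.00 + 24.00 = 25.2 min. At b = 10%: 0.9 × 25.24 + 0.1 × 0.167 = 22.7 min. The share recorded at 10 s rises from 10% to 0.9 × 10% + 10% = 19%.

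The Kaplan-Meier median is less sensitive. In the nose profile the cumulative share with cooling is 40% at 1 min and 60% at 5 min, so the median is 5 min. At b = 10% these become 0.9 × 40% + 10% = 46% and 0.9 × 60% + 10% = 64%, and the median stays at 5 min. At b = 20% the 1-minute share becomes 0.8 × 40% + 20% = 52%, and the median moves to 1 min.

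**Duration.** Section 10.3 does not say whether duration is the last 'yes' or the last minus the first. Take one affected participant with true onset 1 min and true last 'yes' 20 min:

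- Background gone by 5 min: last 'yes' stays at 20 min; last minus first goes from 19 to 20 − 0.17 = 19.8 min.
- Background to 30 min: last 'yes' becomes 30 min; last minus first becomes 29.8 min.
- No tablet cooling at all, background to 10 min: about 10 min is credited under either definition.

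Under the last-'yes' definition, then, background cooling adds duration only if it outlasts the tablet's cooling or the tablet gives none. The worst case, background ticked at every reading to 60 min, gives a mean of (1 − b) × D + b × 60 for a true mean D. At b = 5%: D = 10 gives 12.5 min, D = 15 gives 17.3 min, D = 20 gives 22 min.

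**The case against.** The strongest reply is that the plan already closes the obvious sources. Food, candy, gum, tooth-brushing and drinks other than water are barred for an hour. Water is barred during testing. Congested participants, and those with conditions affecting taste or temperature perception, are excluded (6.2). Where onset is fast, as it may be in the mouth, the shift is a matter of seconds. All of this stands, and it limits the size. It does not supply the missing reading.

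A reader might also infer more than the documents support:

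- *That permitted allergy medicines go unrecorded.* Inclusion 4 admits people "symptomatic and treating with an allergy medicine that is not an antihistamine", but section 8 requires every medicine in use to be recorded with reason, dates, dose and frequency. Only the clock time of last use is absent. Nothing in the documents says that these medicines cause cooling.
- *That the on-site check overlooks drinks.* The list in 9.2.1 ("eating food or candy, chewing gum, or brushing teeth within one (1) hour prior to enrollment on testing day") is introduced as an example, and the same list includes a review of eligibility, which covers inclusion 7 and its limit on liquids.
- *That claimed duration is inflated by the worst-case amounts.* Those figures need background cooling to persist for the full hour. Nothing in the documents suggests that cold water or mouthwash would do so.
- *That the bias can only favour the product.* This holds for onset. It is not shown for duration: the 60-minute imputation is stated after both variables, and if it also applied to duration, background cooling in a never-perceiver would replace 60 by a shorter time. It is not shown for the agreement items either, since someone already cool might notice less added effect.
- *That the primary result is undermined.* The primary item asks what the product provides, which attributes the sensation to the tablet.

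Two allergy-questionnaire items and section 9.4.3 are redacted and cannot be checked, but the cooling row of the schedule is visible and has no Baseline mark.

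**Conclusion.** The point holds as a gap in the timed secondary outcomes, chiefly onset. Without a pre-dose reading or a comparator, pre-existing cooling that is still felt at 10 seconds is scored as a 10-second onset.

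The size is unknown because it depends on an assumed b. At 5% it is negligible when true onset is 1 min (0.04 min), small at 5 min (0.24 min), and up to 2.99 min if those affected would otherwise be imputed at 60 min. It therefore matters most in any location where many participants never perceive cooling from the tablet. The effect on duration depends on which definition is used and on how long the background lasts. The primary agreement percentage is less exposed, and a sensitivity analysis is enough there. This is an inexpensive improvement to make before the study starts, not a flaw that invalidates the design.

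**What to change.** - Add a 'Before dose' row to the 9.4.1 form and a mark for the cooling assessment under Baseline in 9.1.
- In 10.3, report the number with pre-dose cooling by location. Give onset and duration per location for participants with no pre-dose cooling there, next to the all-participant figures.
- Repeat the primary percentage and its 95% confidence interval without pre-dose positives, as a sensitivity analysis.
- Add mouthwash, breath sprays, breath strips and similar mint or menthol products to the one-hour list in 6.3 and inclusion 7.

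The cost is one form row, about 10 seconds per participant, and a few words of text. There are two downsides. Asking about cooling before dosing adds slight cueing; 9.2.4 does not describe the training content, so one cannot assume that participants are already cued, but the same question follows 10 seconds after dosing in any case. A few participants also leave the location-specific timing figures (20 of 400 at b = 5%), which is why the all-participant figures should be kept alongside. If pre-dose cooling proves close to zero, the new row supports the onset claim.

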**9.4.2 Sensory Attributes Questionnaire**

Participants will be instructed to complete the questionnaire as following:

“Please indicate to what level you agree or disagree with the corresponding statement:”

Question	Strongly agree (5)	Somewhat agree (4)	Neither agree nor disagree (3)	Somewhat disagree (2)	Strongly disagree (1)
The product provides a cooling sensation					
The product provides a cooling sensation in the mouth					
The product provides a cooling sensation in the nose					
The product provides a cooling sensation in the throat					
The product provides a refreshing sensation					
The product provides a refreshing sensation in the mouth					
The product provides a refreshing sensation in the nose					
The product provides a refreshing sensation in the throat					
The product tastes great					
The product experience was enjoyable					

I like the flavor sensation of the product					
The product feels soothing on the throat					
The sensory experience is unique for an allergy medicine					
The cooling sensation is refreshing					

9.4.3 CCI [REDACTED]

[REDACTED]

[REDACTED]

[REDACTED]

[REDACTED]

## 9.5 Adverse Events

### 9.5.1 Definition of AE

#### AE Definition

- An AE is any untoward medical occurrence in a patient or clinical study participant, associated with the use of study intervention, whether or not considered related to the study intervention.
- NOTE: An AE can therefore be any unfavorable and unintended sign (including an abnormal laboratory finding), symptom, or disease (new or exacerbated) associated with the use of study intervention.

#### Events Meeting the AE Definition

- Any abnormal laboratory test results (hematology, clinical chemistry, or urinalysis) or other safety assessments (eg, ECG, radiological scans, vital signs measurements), including those that worsen from baseline, considered clinically significant in the medical and scientific judgment of the investigator.
- Exacerbation of a chronic or intermittent pre-existing condition including either an increase in frequency and/or intensity of the condition.
- New conditions detected or diagnosed after study intervention administration even though it may have been present before the start of the study.
- Signs, symptoms, or the clinical sequelae of a suspected drug-drug interaction.
- Signs, symptoms, or the clinical sequelae of a suspected overdose of either study intervention or a concomitant medication. Overdose per se will not be reported as an AE/SAE unless it is an intentional overdose taken with possible suicidal/self-harming intent. Such overdoses should be reported regardless of sequelae.
- The signs, symptoms, and/or clinical sequelae resulting from lack of efficacy will be reported as AE or SAE if they fulfil the definition of an AE or SAE. Also, “lack of efficacy” or “failure of expected pharmacological action” also constitutes an AE or SAE.

#### Events NOT Meeting the AE Definition

- Any clinically significant abnormal laboratory findings or other abnormal safety assessments which are associated with the underlying disease, unless judged by the investigator to be more severe than expected for the participant’s condition.
- The disease/disorder being studied or expected progression, signs, or symptoms of the disease/disorder being studied, unless more severe than expected for the participant’s condition.

- 
- Medical or surgical procedure (eg, endoscopy, appendectomy): the condition that leads to the procedure is the AE.
  - Situations in which an untoward medical occurrence did not occur (social and/or convenience admission to a hospital).
  - Anticipated day-to-day fluctuations of pre-existing disease(s) or condition(s) present or detected at the start of the study that do not worsen.
- 

### 9.5.2 Definition of SAE

**An SAE is defined as any untoward medical occurrence that, at any dose:**

**a. Results in death**

**b. Is life-threatening**

- The term 'life-threatening' in the definition of 'serious' refers to an event in which the participant was at risk of death at the time of the event. It does not refer to an event, which hypothetically might have caused death, if it were more severe.

**c. Requires inpatient hospitalization or prolongation of existing hospitalization**

- In general, hospitalization signifies that the participant has been detained (usually involving at least an overnight stay) at the hospital or emergency ward for observation and/or treatment that would not have been appropriate in the physician's office or outpatient setting. Complications that occur during hospitalization are AEs. If a complication prolongs hospitalization or fulfills any other serious criteria, the event is serious. When in doubt as to whether "hospitalization" occurred or was necessary, the AE should be considered serious.
- Hospitalization for elective treatment of a pre-existing condition that did not worsen from baseline is not considered an AE.

**d. Results in persistent disability/incapacity**

- The term disability means a substantial disruption of a person's ability to conduct normal life functions.
- This definition is not intended to include experiences of relatively minor medical significance such as uncomplicated headache, nausea, vomiting, diarrhea, influenza, and accidental trauma (eg, sprained ankle) which may interfere with or prevent everyday life functions but do not constitute a substantial disruption.

**e. Is a congenital anomaly/birth defect**

**f. Other situations:**

- Medical or scientific judgment should be exercised in deciding whether SAE reporting is appropriate in other situations such as important medical events that may not be immediately life-threatening or result in death or hospitalization but may jeopardize the participant or may require medical or surgical intervention to prevent one of the other outcomes listed in the above definition. These events should usually be considered serious.
-

- 
- Examples of such events include invasive or malignant cancers, intensive treatment in an emergency room or at home for allergic bronchospasm, blood dyscrasias or convulsions that do not result in hospitalization, or development of drug dependency or drug abuse.
- 

### 9.5.3 Recording and Follow-Up of AE and/or SAE

#### AE and SAE Recording

- When an AE/SAE occurs, it is the responsibility of the investigator to review all documentation (eg, hospital progress notes, laboratory reports, and diagnostics reports) related to the event.
- The investigator will then record all relevant AE/SAE information in the CRF.
- It is not acceptable for the investigator to send photocopies of the participant's medical records in lieu of completion of the AE/SAE CRF page.
- There may be instances when copies of medical records for certain cases are requested. In this case, all participant identifiers, with the exception of the participant number, will be redacted on the copies of the medical records before submission.
- The investigator will attempt to establish a diagnosis of the event based on signs, symptoms, and/or other clinical information. Whenever possible, the diagnosis (not the individual signs/symptoms) will be documented as the AE/SAE.

